## 2 Objectives, endpoints and estimands

**Table 2-1 Objectives and related endpoints**

Objective(s)	Endpoint(s)
Primary Objectives	Endpoint(s) for primary objective(s)

 
To assess immune response to non-live mRNA COVID-19 vaccine in ofatumumab treated participants
 
	
 
Achieving immune response as defined by positive SARS-CoV-2 qualitative IgG antibody assay <math>\geq</math> 14 days after vaccination (yes/no)
 

Secondary Objectives	Endpoint(s) for secondary objective(s)

 
To assess sustained immune response to non-live mRNA COVID-19 vaccine in ofatumumab treated participants
 
To assess immune conversion to non-live mRNA COVID-19 vaccine in ofatumumab treated participants
 
	
 
Achieve immune response at other assessment time points (yes/no)
 
Immune conversion to non-live mRNA COVID-19 vaccine (yes/no) defined as : 
 
For patients with serum available prior to vaccine: 
 
Baseline absence of SARS-CoV-2 spike IgG with post-vaccination SARS-CoV-2 positive qualitative antibody assay <math>\geq</math> 14 days after full course (two doses) vaccination (yes/no) or
 
Baseline serum presence of SARS-CoV-2 quantitative IgG antibody with post-vaccination <math>\geq</math> 4-fold increase in SARS-CoV-2 quantitative antibody titer as determined by dilution assay <math>\geq</math> 14 days after vaccination (yes/no)
 
 
 
For patients with serum unavailable prior to vaccine but who have not received a booster (Cohorts 4 and 5): 
 
Initial negative SARS-CoV-2 nucleocapsid antibody with post-vaccination SARS-CoV-2 positive qualitative antibody assay <math>\geq</math> 14 days after full course (two doses) vaccination (yes/no)
 
 
 
 
 

 
To assess adverse events and serious adverse events
 
	
 
Adverse events/serious adverse events
 

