### **Duration of treatment:**

The treatment duration is 382 days for those receiving the Pfizer mRNA vaccine and 389 days for those receiving the Moderna mRNA vaccine. This duration is chosen to provide long term information regarding vaccine response and safety outcomes.

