2.6.1 Secondary endpoint(s)

Secondary endpoints include the following:

- Achieving immune response (responder) as defined by a positive SARS-CoV-2 qualitative IgG antibody assay at other assessment time points ≥ 14 days after full course (2 doses) vaccination (yes/no).
- Immune conversion (yes/no) which is defined as:
 - Pre-vaccination absence of SARS-CoV-2 qualitative IgG antibody with post-vaccination positive SARS-CoV-2 qualitative IgG antibody assay at any assessment time point ≥ 14 days after full course (2 doses) vaccination (yes/no); or
 - Pre-vaccination serum presence of SARS-CoV-2 quantitative IgG antibody with post-vaccination ≥ 4 -fold increase in SARS-CoV-2 quantitative antibody titer as determined by dilution assay at any assessment time point ≥ 14 days after full course (2 doses) vaccination (yes/no); or
 - Initial negative SARS-CoV-2 nucleocapsid antibody at Visit 2 (Day 1) with post-vaccination positive SARS-CoV-2 qualitative IgG antibody assay at any post-Visit 2 (Day 1) assessment time point ≥ 14 days after full course (2 doses) vaccination (yes/no) (Applicable to Cohorts 4 and 5.)

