2.6.2 Statistical hypothesis, model, and method of analysis

The number and percentage of responders will be presented by cohort group (and overall) and time point (where appropriate). The 2-sided 95% CI for the proportion of responders will be calculated using an exact method ([Clopper and Pearson, 1934](#)). Participants achieving immune conversion will be summarized in a similar fashion.

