2.6.3 Handling of intercurrent events

NRI approach will be applied to missing antibody assay regardless of intercurrent events.

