2.6.6 Supplementary analyses

A supplemental analysis of each secondary endpoint will be performed using an observed case approach (completers) by using valid assessments of antibody assay without imputation of missing data.

In addition, analysis of secondary endpoints will be repeated using data from Cohort 6 participants and any participants in Cohorts 1 – 5 who received an mRNA booster during the study. Missing antibody assay will be handled according to the NRI approach.

The number and percentage of responders will be presented by cohort group and overall. The 2-sided 95% CI for the proportion of responders will be calculated using an exact method ([Clopper and Pearson, 1934](#)). Participants achieving immune conversion will be summarized in a similar fashion.

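### In the visible text, the sustained-response objective is served only by separate percentages positive at each visit, which do not show whether initial responders stay positive

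*Protocol*

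**What the plan says.** Among the secondary objectives in Protocol Table 2-1 is "To assess sustained immune response to non-live mRNA COVID-19 vaccine in ofatumumab treated participants". The endpoint set against it is "Achieve immune response at other assessment time points (yes/no". SAP Table 1 repeats this pairing, and SAP 2.6.1 defines the endpoint as "Achieving immune response (responder) as defined by a positive SARS-CoV-2 qualitative IgG antibody assay at other assessment time points", from 14 days after the second dose onward. Immune conversion is listed as a separate objective with its own endpoint.

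SAP 2.6.2 gives the summary: "The number and percentage of responders will be presented by cohort group (and overall) and time point (where appropriate", and "The 2-sided 95% CI for the proportion of responders will be calculated using an exact method". On missing data, SAP 2.6.3 states: "NRI approach will be applied to missing antibody assay regardless of intercurrent events". SAP 2.6.6 adds an analysis of each secondary endpoint "performed using an observed case approach (completers) by using valid assessments of antibody assay without imputation of missing data", and a repeat restricted to Cohort 6 plus anyone in Cohorts 1 to 5 boosted during the study. Neither document specifies a secondary estimand.

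Follow-up runs to Day 382 (Pfizer) or Day 389 (Moderna). Protocol 4.2 explains why: "This duration is chosen to provide long term information regarding vaccine response and safety outcomes".

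**The concern.** A sustained response is a property of one participant over time: positive at the primary time point and positive again later. The planned endpoint asks only whether a participant is positive at a given later visit. Someone negative at first and positive at Day 292 counts toward it and offsets someone who was positive and became negative. The conversion endpoint does not fill the gap, because SAP 2.6.1 counts a positive result at any qualifying time point.

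Late positives have a foreseeable source. Protocol 12.5 expects some participants to be boosted during the trial. A booster is not listed as an intercurrent event, and nothing in the main per-visit tables excludes results that follow one. Losses through missing data are foreseeable too. A 10% dropout is planned, and Protocol 8.5.2 and 9.1.2 require withdrawal for low IgG, so missing assays may be related to immune status.

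Cohort 1 has most at stake. Its primary sample is taken before the first ofatumumab dose (Protocol 6.3.2 and 8), and later samples are taken on treatment. Retention among its initial responders is the most direct description of what happens to an established response once ofatumumab starts, and the planned tables do not show it.

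**Working it through.** **The plan's own figures.** Protocol 12.8.1 gives half-widths of 20.1%, 19% and 17.5% for n = 20 at response rates of 70%, 75% and 80%. The formula 1.96 × √(p(1−p)/20) gives 20.08%, 18.98% and 17.53%, so they reproduce. These rates imply 14, 15 or 16 responders among 20. Each cohort group enrols 22, of whom 2 are expected to drop out. The counts below are assumptions chosen near these rates, since the documents give no data on switching.

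**Step 1: can equal percentages hide losses?** Let N participants be assayed at both visits, with R positive each time. If L initial responders become negative, L initial negatives must have become positive, so L cannot exceed N − R. Retention is (R − L)/R, and its minimum is max(0, 2R − N)/R.

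For N = 22 and R = 15, both visits report 15/22 = 68.2% (exact 95% CI 45.1 to 86.1). Retention depends on the switching:

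| Lose / gain | Initial responders still positive | Exact 95% CI |
|---|---|---|
| 0 / 0 | 15/15 = 100% | 78.2 to 100 |
| 2 / 2 | 13/15 = 86.7% | 59.5 to 98.3 |
| 4 / 4 | 11/15 = 73.3% | 44.9 to 92.2 |
| 7 / 7 (maximum) | 8/15 = 53.3% | 26.6 to 78.7 |

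At R = 17 (77.3% at both visits) the minimum is 12/17 = 70.6%. At R = 11 (50%) it is 0/11. The planned output is identical across each range.

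**Step 2: can dropout look like waning?** Assume that nobody loses or gains positivity and that 2 of 22 drop out after the primary time point.

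| Initial rate | Who drops out | Later rate, imputed as non-response | Later rate, observed cases |
|---|---|---|---|
| 15/22 = 68.2% | 2 responders | 13/22 = 59.1% | 13/20 = 65.0% |
| 16/22 = 72.7% | 2 responders | 14/22 = 63.6% | 14/20 = 70.0% |
| 17/22 = 77.3% | 2 responders | 15/22 = 68.2% | 15/20 = 75.0% |
| 15/22 = 68.2% | 2 non-responders | 15/22 = 68.2% | 15/20 = 75.0% |

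With both dropouts responders, imputation shows an apparent loss of 9.1 points in each case. Observed cases reduce this to 3.2, 2.7 and 2.3 points. If both dropouts were non-responders, observed cases show a gain of 6.8 points that did not occur. The repeat corrects most of the artefact but compares visits with different denominators.

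**Step 3: what does following initial responders add?** In the first row of the second table, retention is 13/13 = 100% among those assayed and 13/15 = 86.7% with missing counted as not positive. The pair shows at once that the whole difference is missing data.

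**The case against.** The strongest reply is that percentage positive over time, with exact intervals and two treatments of missing data, is a legitimate population-level description of durability and is the endpoint the protocol chose. That stands. A reader might infer that the objective goes unanswered or that the planned tables are invalid. The documents do not support that: the tables answer a population question, but not the one about initial responders.

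A second reply is that the dropout problem is already handled. That is largely true, as step 2 shows. The inference that dropout will pass for waning unnoticed ignores the observed-case repeat. Nor is every missing assay scored as a lost response, since an initial non-responder with a missing assay had none to lose.

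Third, the late-conversion counts are invented, and the one named source of late positives, boosters, gets a further analysis (Protocol 12.5, SAP 2.6.6). The counts are indeed illustrative. The booster analysis, however, is an added subset: it does not remove post-booster results from the main tables, and it does not link visits.

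Fourth, SAP 2.1 provides for listing all data, so retention could be counted afterwards. It could, but without a definition or denominator fixed in advance.

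Fifth, Protocol 12.6 and SAP 2.12 are not visible. A reader might infer that no linked analysis exists anywhere; only its absence from the visible text can be asserted.

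Finally, the Protocol summary does not list sustained response among the secondary objectives. Protocol Table 2-1 and SAP Table 1 both do.

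**Conclusion.** The point holds as an objective-to-analysis mismatch that should be repaired. In the visible text nothing reports whether participants positive at the primary time point stay positive, and the planned percentages cannot recover it. With 22 participants and 68.2% positive at both visits, retention could lie anywhere from 53.3% to 100%. The dropout component is secondary: about 9 points under imputation and about 2 to 3 points in observed cases, if both planned dropouts are responders.

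These sizes rest on assumed counts. They show what the tables cannot distinguish, and they do not predict how much switching will occur.

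One further inference should be resisted. Retention in Cohort 1 might be read as ofatumumab's effect on an established response. Allocation is not randomised (Protocol 6.4.1.1), and a single-cohort table cannot separate ofatumumab from natural waning.

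Initial response also means different things across cohorts. For Cohorts 4 to 6 the primary time point is Visit 2, which can fall at any time from two weeks after vaccination or booster. Some participants may already have lost a response by then and would not enter the denominator.

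**What to change.** In SAP 2.6, keep the planned percentages and add one descriptive cross-table per cohort group: status at the primary time point (positive, negative) by status at each later scheduled visit (positive, negative, missing).

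- Report the number and percentage of initial responders who are positive at that visit, with an exact 95% CI, first among those assayed and then with missing counted as not positive.
- Show late converters, negative then positive, in a separate row.
- If positivity at every visit so far is also reported, label it as a different quantity. It differs for positive-negative-positive patterns, and it needs its own rule for missed intermediate visits.
- Flag results obtained after an on-study booster and give the table with and without them.
- Show Cohorts 4 and 5 separately from Cohorts 2 and 3, because their first sample may be long after vaccination. Read Cohort 6 with the same caution.
- Describe the Cohort 1 table as retention after ofatumumab start, set beside the interferon or glatiramer acetate group, with no causal claim.

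The cost is one extra table from assays already scheduled. The downside is imprecision: with about 14 to 16 initial responders per group, 10/14 = 71.4% has an exact 95% CI of about 42% to 92%. Splitting the combined groups widens the intervals further.

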## 2.1 Primary estimands

The estimand is the precise description of the treatment effect and reflects strategies to address events occurring during the trial conduct which could impact the interpretation of the trial results (e.g., premature discontinuation of treatment).

The primary clinical question of interest is: Do relapsing MS participants who receive ofatumumab treatment mount an immune response to non-live mRNA COVID-19 vaccine?

The justification for the primary estimand is that it will capture whether ofatumumab treated participants generate antibodies to mRNA COVID-19 vaccines.

The primary estimand is described by the following attributes:

- **Population:** Defined through appropriate inclusion/exclusion criteria to reflect the targeted population. Relapsing MS participants subdivided into 6 cohorts. (1) Will receive a full course (two doses) of a COVID-19 mRNA vaccine two weeks prior to starting ofatumumab 20 mg subcutaneous treatment; (2) Will receive a full course (two doses) of a COVID-19 mRNA vaccine after at least 4 weeks of commercial ofatumumab 20 mg subcutaneous treatment (3) Will receive a full course (two doses) of a COVID-19 mRNA vaccine after at least 4 weeks of interferon or glatiramer acetate treatment (4) Completed a full course (two doses) of a COVID-19 mRNA vaccine after at least 4 weeks of commercial ofatumumab 20 mg subcutaneous treatment but has not yet received a COVID-19 mRNA booster (5) Completed a full course (two doses) of a COVID-19 mRNA vaccine after at least 4 weeks of interferon or glatiramer acetate (may or may not have received at least 1 COVID-19 mRNA booster) (6) Completed a full course (two doses) of a COVID-19 mRNA vaccine after at least 4 weeks of commercial ofatumumab 20 mg subcutaneous treatment and received at least 1 additional booster vaccine  $\geq$  14 days prior to Screening.
- **Variable:** Achieving immune response as defined by a positive SARS-CoV-2 qualitative IgG antibody assay  $\geq$  14 days after full course (two doses) vaccination (yes/no)
- **Treatment of interest:** Non-live COVID-19 mRNA vaccine either two weeks prior to ofatumumab start or at least 4 weeks after ofatumumab start or while on interferon or glatiramer acetate
- **Intercurrent event:** Discontinuation of treatment/study, or death
- **Summary measure:** Proportion of participants achieving immune response

## 2.2 Secondary estimands

Not applicable.

### 3 Study design

This is a 6-cohort, multicenter prospective study in up to 88 participants with relapsing multiple sclerosis. Up to 66 of the participants will begin treatment with ofatumumab or already be on commercial ofatumumab, the remaining 22 participants will remain on interferon or glatiramer acetate.

In this study, participants must intend to receive or have received a full course of a non-live COVID-19 mRNA (Pfizer or Moderna) vaccine. Participants also must meet inclusion criteria and not meet exclusion criteria.

#### 1. Screening Period:

Participants will enter a Screening Period of up to 7 days to assess eligibility requirements. Participants in Cohort 1, 2, 4 and 6 without Hepatitis B virus (HBV) and total serum immunoglobulin results within the past 6 months prior to screening will require central labs drawn. Participants with Hepatitis B virus (HBV) and total serum immunoglobulin results within the specified inclusion range the past 6 months prior to screening will not require the labs to be drawn.

Participants in Cohort 3 and 5 without total serum immunoglobulin results within the past 6 months prior to screening will require central labs drawn. Participants with total serum immunoglobulin results within the specified inclusion range the past 6 months prior to screening will not require the labs to be drawn.

#### 1. Treatment Period:

Participants will obtain the mRNA vaccine through their HCP (private insurance) or appropriate federal, state or local program. Participants should be instructed to provide documentation of vaccine administration to the Study Doctor at the next scheduled on-site study visit.

##### Cohort 1:

For participants who receive the Pfizer vaccine, the first of three 20 mg s.c ofatumumab loading doses will be administered on Day 36 or 2 weeks after receiving a full course (two doses) of a COVID-19 vaccine. The 2nd and 3rd loading doses should be administered on Day 43 and Day 50 or 7 and 14 days respectively after the 1st loading dose. Subsequent dosing includes 20 mg s.c. administered monthly starting at Day 64.

For participants who receive the Moderna vaccine, the first of three 20 mg s.c ofatumumab loading doses will be administered on Day 43 or 2 weeks after receiving a full course (two doses) of a COVID-19 vaccine. The 2nd and 3rd loading doses should be administered on Day 50 and Day 57 or 7 and 14 days respectively after the 1st loading dose. Subsequent dosing includes 20 mg s.c administered monthly starting at Day 71.

**Cohort 2:** Will continue taking their prescribed ofatumumab as per their current dosing schedule.

**Cohort 3:** Will continue administration of their prescribed interferon or glatiramer acetate as per their current dosing schedule.

[figure not shown]
**Cohort 4:** Will continue taking their prescribed ofatumumab as per their current dosing schedule and should adhere to the visit schedule as shown in either [Table 8-5](#) (Pfizer) or [Table 8-6](#) (Moderna).

**Cohort 5:** Will continue taking their prescribed glatiramer acetate or interferon as per their current dosing schedule and should adhere to the visit schedule as shown in either [Table 8-5](#) (Pfizer) or [Table 8-6](#) (Moderna).

[figure not shown]
**Cohort 6:** Will continue taking their prescribed ofatumumab as per their current dosing schedule and should adhere to the visit schedule as shown in either [Table 8-5](#) (Pfizer) or [Table 8-6](#) (Moderna).

[figure not shown]
Study design schematics for Cohorts 1, 2 and 3 are shown in [Figure 3-1](#), [Figure 3-2](#), [Figure 3-3](#), and [Figure 3-4](#). Study design schemas for Cohorts 4, 5, and 6 are shown in [Figure 3-5](#) and [Figure 3-6](#).

[figure not shown]
[figure not shown]
[figure not shown]
**Figure 3-1 Study Design (Cohort 1, Pfizer)**

**Figure 3-2 Study Design (Cohort 1, Moderna)**

**Figure 3-3      Study Design (Cohorts 2 and 3, Pfizer)**

**Figure 3-4 Study Design (Cohorts 2 and 3, Moderna)****Figure 3-5 Study Design (Cohorts 4, 5, and 6, Pfizer)****Figure 3-6 Study Design (Cohorts 4, 5, and 6, Moderna)**

## Remote procedures

At the investigator's direction and based on benefit-risk considerations of the participant's clinical condition, qualifying participants may be offered the option to have certain clinical trial procedures according to the assessment schedules in [Table 8-1](#), [Table 8-2](#), [Table 8-3](#), [Table 8-4](#), [Table 8-5](#) and [Table 8-6](#) performed from within their home.

Such procedures will be performed remotely under the oversight of the Investigator, who retains accountability for the oversight and all efficacy and safety decisions with delegation of tasks to an off-site healthcare professional. Off-site healthcare professionals will be provided by a third-party vendor sourced by Novartis or an agent for Novartis.

In addition to procedures performed by the off-site healthcare professional, the on-site staff may perform certain procedures remotely using tele-visits.

## 4 Rationale

### 4.1 Rationale for study design

A multicenter, 6-cohort, open-label, comparator design has been selected in order to render feasible recruitment given the study's expedited schedule based on the importance of this dataset. The study will address two questions:

1. Can participants treated with ofatumumab develop an immune response if receiving a COVID-19 mRNA vaccine two weeks prior to ofatumumab start?
2. If receiving COVID-19 mRNA vaccine after introduction of ofatumumab treatment, can participants develop an immune response?

[figure not shown]
Participant Cohorts 3 and 5 on interferon or glatiramer acetate are included as a comparator.

#### Rationale of study population:

The included population is selected to be consistent with the ofatumumab phase 3 trial program and within the parameters of use specified by FDA approval and United States Prescribing Information (USPI). Screening participants will be excluded if they possess contraindications to either receiving ofatumumab per prescribing information or they possess contraindications to receiving a COVID-19 mRNA vaccine. Participants will also be excluded if there is clinical or serologic evidence, they have already contracted COVID-19. This is appropriate because the aim of the study is to assess whether a non-vaccinated ofatumumab treated individual can mount a response after COVID-19 mRNA vaccine.

#### Rationale of chosen endpoints:

Whether or not participants develop an immune response to the mRNA COVID-19 vaccine they receive will be determined by serum immune measures of humoral and cell mediated responses. Currently there is no consensus on which assays, and values would indicate seroprotection or seroconversion. Notwithstanding this, testing is available to consider both arms of the immune response. Here we propose to use a serum qualitative IgG SARS coV2 antibody assay to measure the humoral response. The qualitative IgG SARS CoV2 assay has received an emergency use approval from the FDA.

## **4.2 Rationale for dose/regimen and duration of treatment**

### **Ofatumumab dose**

The dose regimen for ofatumumab in this study is consistent with the FDA approved regimen in the prescribing information.

### **Duration of treatment:**

The treatment duration is 382 days for those receiving the Pfizer mRNA vaccine and 389 days for those receiving the Moderna mRNA vaccine. This duration is chosen to provide long term information regarding vaccine response and safety outcomes.

